7.4. Concomitant treatment

Concomitant treatment, including medication, will be registered in the CRF.

Subjects are not allowed to use barrier cream or barrier film during the investigation.

The skin undergoes major changes during radio- and or chemotherapy, and the skin might get more fragile to product changes. Therefore, subjects are not allowed to receive radio- and/or chemotherapy during the investigation

- low doses chemotherapy is allowed for indications other than cancer

Steroid products on peristomal skin may interfere with the skin condition and use can make the skin more fragile to change of baseplates. Therefore, subjects are not allowed to use topical steroid treatment in the peristomal skin area e.g.

- Low dose systemic steroid treatment (e.g. inhalation) assessed by the investigator are allowed.
- Other systemic steroid treatment (e.g. injection, or tablet) are not allowed.

8. Risk – benefit analysis

8.1. Risk-benefit analysis of the Coloplast investigational product

A number of risks connected to use of the test product have been identified in the Product Risk Assessment. All risks will be mitigated before release of products for the clinical investigation. The risk management process has been performed in accordance with the requirements stated in ISO 14971:2012 and in accordance with internal Coloplast procedures, including design verification, validated test methods, risk analysis and completion of a biological report for the test product.

The following risks will be mitigated by actions during the clinical investigation.

- **Irritated skin (intact or non-intact):** Incorrect use of the product can lead to intact or non-intact irritated skin.
- **Tissue necrosis around the stoma:** Products with too small hole due to incorrect custom-cut, could lead to a squeezed stoma and therefore tissue necrosis around stoma.

CONFIDENTIAL

To mitigate and reduce the risks, the users will be trained, according to the IFU, in preparation of the product (e.g. hole size), preparation of skin before application (e.g. cleaning and wiping), application of product (e.g. correct position and applying pressure to the baseplate), removal of product and storage of the product.

Risks have been proven minimized or eliminated through appropriate design control, confirmed by pre-clinical bench, laboratory and animal testing.

8.2. Risk-benefit analysis for the conduct of the clinical investigation

The test products contain a [REDACTED] the skin from leakage induced skin damage, which could be beneficial for the subjects. The outcome of this investigation will contribute with important information for development of products for subjects with a stoma, regarding [REDACTED] the skin from leakage induced skin damage.

Disadvantages during the investigation could be the extra workload related to completion of questionnaires, visits at site and using the clinical app at each change of product. The subjects are also asked to use a CE-marked competitor product for the comparator test period that may not be their preferred product on the market.

The participating subjects will contribute with important information for development of new stoma products, that may have less negative impact on the peristomal skin. Due to the actions taken to mitigate the above-mentioned risks, the risks and disadvantages when participating in this clinical investigation are estimated as low. The subject's health will not benefit directly from this investigation, but they may benefit from the use of the new stoma product through less irritated peristomal skin and improved quality of life in the future.

A risk assessment of the clinical investigation will be conducted initially prior to the first subject enrolment and periodically re-assessed based on any new risks identified through the process. This assessment will be completed throughout the duration of the investigation. A risk-based monitoring strategy will be used including on-site, remote, and central monitoring. Details of the strategy are defined in the monitoring plan.

9. Monitoring

The data collected throughout the investigation and the conduct of the investigation, will be monitored to ensure and verify, that the rights and well-being of the subjects are protected, that the reported data are accurate, complete, and verifiable from source documents, and that the conduct of the investigation complies with the approved CIP, subsequent amendment(s), ISO14155/ and the applicable regulatory requirement(s).

The monitoring process is briefly described below and is described in details in the Monitoring Plan.

The monitoring will be conducted periodically at all sites by qualified designee personnel. The monitoring of this clinical investigation in Netherlands and Italy has been delegated by the sponsor to [REDACTED]. The investigator must be available for and agrees to cooperate with Coloplast Clinical Managers (CM) and/or CRO Clinical Research Associates' (CRA) during their visits and ensure that they have direct access to all documents that they require, including direct access to the subjects' files.

The investigation will be subject to internal audits if relevant. All monitoring visits and possible audits will be followed by internal reports and corrective actions, if needed. Follow-up letters will be forwarded to sites after all visits and any findings should be addressed by the investigator or designee.

To ensure proper conduct of the investigation the following visits on site will be performed during the investigation:

- Site selection visit
- Site Initiation Visit

CONFIDENTIAL

- Periodic Monitoring visits
- Close Out visit

9.1. Periodic Monitoring visit(s)

Periodic Monitoring visit on site will be performed as soon as reasonable possible, after the site has enrolled the first subject in the investigation. This visit must be planned in order to up front minimise systematic errors done by site or subjects.

A monitoring visit on site will be performed after all subjects on site have completed the investigation. The CM/CRA shall have close contact to the Principal Investigators/sites during the conduct of the investigation, to ensure that any concerns, problems or recruitment challenges are solved with the site in a timely manner. If further monitoring visits on site or calls with site are required, this will be effectuated as needed.

Centralised monitoring reviewing data entered in the eCRF and the Subject's Clinical Trial App, will be performed by Coloplast CM throughout the conduct of the investigation.

The CRO CRA shall inform the sponsor about any problems relating to facilities, technical equipment or site personnel at the clinical investigation site. During the clinical investigation, monitors shall check that appropriate written informed consents have been obtained. The monitor shall also be responsible for notifying such deficiencies in writing to the principal investigator and convene with the clinical investigation site personnel appropriate and timely corrective actions.

10. Source data verification

A source document is a document in which data collected for a clinical trial is first recorded. This data is usually later entered in the electronic case report form (eCRF). Source documents are defined as "original documents, data, and records. In some cases, the eCRF can be the source document. Source documents contain source data, which is defined as all information in original records and certified copies of original records of clinical findings, observations, or other activities in a clinical trial necessary for the reconstruction and evaluation of the trial.

All documents and data related to the clinical investigation handled by site personnel, shall be produced and maintained in a way that assures reliability, integrity, control and traceability, and shall be appropriately stored to provide a complete history.

The Principal Investigator shall assure the accuracy, attribution, completeness, legibility and timeliness of the data reported to the sponsor in the eCRFs and in all required reports. All printed copies of electronic source documents shall be certified, as indicated by a dated signature by the investigational site personnel at the time the document is printed. Special requirements should be applied to the capture, review and retention of electronic source data, to ensure reliability, quality, integrity and traceability.

The data reported in the eCRFs shall be derived from source documents and be consistent with these source documents, and any discrepancies shall be explained in writing. In some cases, the eCRF can serve as the source document and this must be documented on the Source Data Specification Form. The Source Data Specification Form must be completed at the initiation visit detailing the location of the source data for each data point.

Only the Principal Investigator, delegated site personnel and the sponsor representatives will have access to all the eCRFs. The subject will have access to questionnaires and diaries completed in the Clinical Trial App.

CONFIDENTIAL

11. Statistical considerations

11.1. Statistical design, method and analytical procedures

The primary objective will be evaluated by analysing the primary and secondary endpoints. These analyses are carried out by Medical Affairs, Coloplast A/S and are described in the following. The secondary objective regarding the [REDACTED] will be evaluated out by [REDACTED] and [REDACTED]

All baseline measurements, endpoints and other measurements (see Appendix 1 - Endpoints) will be summarized by descriptive statistics and/or listed. Endpoints and other measurements will be summarized by product, product type (1- or 2-pc) and visit, if relevant. Descriptive statistics for continuous variables are presented with N, Mean, SD (standard deviation), Median, Min and Max), where N denotes the number of subjects contributing with non-missing data. For discrete variables, descriptive statistics are presented with N and percentage, where percentage is based on the total number of subjects/observations with non-missing data.

As it is an exploratory study no adjustment for multiple testing will be applied.

All statistical analyses are made with SAS version 9.4 (SAS Institute Inc., Cary, NC)

Definition of analysis populations

Intention to Treat (ITT), Safety and Per Protocol (PP) populations will be defined at a formal data review meeting just before database lock. As a minimum, the data manager, the clinical manager and the statistician will be involved in the classification of subjects.

The ITT population (full analysis set) will be constituted by all randomised subjects with valid informed consent who have been exposed to at least one product, and with valid information on at least one product with respect to either primary or secondary endpoints.

The PP population will be constituted by a subset of ITT subjects who fulfilled the inclusion/exclusion criteria and did not violate the protocol in a serious way

Any exclusion of subjects from the PP/ITT population must be documented. Invalid individual data points may be omitted from analysis even though the corresponding subject is part of the ITT or PP population. Any exclusion of data points will be documented.

The Safety population will constitute by subjects who have given informed consent.

All statistical analysis will be based upon the ITT and PP population whereas adverse events and Device deficiencies will be assessed based on the safety population.

In light of the data obtained it might be considered to make additional explorative analyses based on a subset of the ITT/PP population.

Analysis of the primary endpoint

Max itching score within a week at steady state will be analysed by a mixed repeated measures model using individual week max scores (on a scale from 0-10) as the observational unit. The model will consider that observations corresponding to different subjects are independent; whereas observations corresponding to the same subject are correlated. The correlation between observations corresponding to the same product can be larger than observations corresponding to different products. Hence the model includes a fixed effect of product (comparator product, test product), a fixed effect of product type (1- or 2-pc), a fixed interaction between product and product type, a fixed period effect, an interaction between period and product, a random effect of subject and a random interaction effect of product and subject.

The model might be reduced by removing non-significant fixed effects, if relevant. The interaction between period and product allows for a possible carry-over effect. It is assumed that a possible carry-over effect is the

CONFIDENTIAL

same for 1- and 2-pc users. If the interaction is significant, data from only the first test period will be analysed as a parallel arm study because the first period is free of carry-over effects and period will be excluded from the model.

All combinations of differences between the two products will be estimated for both 1- and 2- pc products. Furthermore, differences for same product between product types will be estimated (if the model is not reduced).

Analysis of the secondary endpoints

The endpoints regarding pain, burning, physical discomfort, ability to move around and the overall ability to stick the baseplate to the skin (on a scale from 0-10) will be analysed by the same model as the primary endpoint starting by calculating the max within a week at steady state.

[REDACTED] endpoints regarding bleeding (Y/N), experiencing any weeping or moisture (Y/N) and Ulcers or sores (Y/N) per baseplate change at steady state will be analysed by a repeated logistic regression model with the same effects included as for the primary endpoint.

The total DET score from Visit 2 and 3 will be analysed by a linear mixed model similar to the model for the primary endpoint, except that the random interaction effect of product and subject is not included, as there is only one measurement per subject for each product. The endpoints regarding individual item scores (discoloration, erosion and tissue overgrowth) can be analysed by the same model, if relevant.

The discoloration area and intensity at steady state will be analysed by the same model as described for the primary endpoint. For these analyses the data from the individual skin photos are the observational unit.

The endpoints regarding frequency in the past 14 days by end of treatment (of itching, pain and burning) will be analysed similar to the analysis of total DET score. Instead of a mixed model, a generalized linear mixed model, namely a proportional odds model, will be applied for the analysis as the response is on a 5-point scale. Proc Glimmix will be applied for the analysis.

Analyses of exploratory endpoints

The leakage area and leakage diameter at steady state will be analyzed by the same model as the discoloration area and intensity described under secondary endpoints.

The median wear time will be analyzed by the same model as the total DET score. The median wear time per subject is based on data from the 3 last weeks in each period.

The three scores from the leakage scale questionnaire (emotional impact, usual/social activities, coping/control) as well as the total score and the sub-scores (discreteness, comfort, confidence and social life) from the quality of life questionnaire will be analyzed by the same model as the total DET score.

The endpoint regarding feeling of security as well as the 3 endpoints regarding handling will be analyzed by the same proportional odds model as described for the frequency of itching in the past 14 days by end of treatment.

The proportion of subjects preferring test product will be compared with the proportion preferring the comparator by a test in the binomial distribution, testing the hypothesis that the proportions are equal.

Analyses of safety endpoints

Adverse events will be listed and summarized, if relevant.

CONFIDENTIAL

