6.3.1. Screening failures

Screening failures are considered subjects that have signed the informed consent form and been included based on in- and exclusion criteria, but not yet randomised.

Subjects that have signed the informed consent form but fails to comply with the in- and exclusion criteria are also considered screening failures.

Screening failures can be replaced by a new subject.

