6.4. Point of enrolment

A subject is considered enrolled in the investigation when the written informed consent is obtained. The expected duration for each subject is described in section 4.1.

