7.1.1. Site visits

Visit 0 (Inclusion visit)

If a potential subject is interested in participating after the first contact, a visit (visit 0) will be arranged in a room reserved to ensure privacy and quiet surroundings at the investigators clinic/department. When arranging the visit, it will be ensured, that the subject has received the Subject Information Form prior to the visit. The subjects will receive both written and verbal information to ensure that the subject understands what was read and explained and can freely agree to participate in the investigation. The subject will, beforehand, also be informed about the possibility of bringing a companion to Visit 0 and to any possible subsequent visits. During the visit the principal Investigator, or delegate, will provide oral information about the investigation based on the Subject Information Form. The subject has the right to wait before deciding on participation.

If/when subjects decide to participate, they will be asked to sign the Informed Consent Signature Form. Hereafter, relevant female subjects will be asked to give a urine sample for a pregnancy test. The sample will be destroyed right after the test. If a subject so desires, and it is certain that it is understood what the investigation entails, and the relevant form has been signed the subjects are considered enrolled in the investigation. Enrolled subjects that are deemed eligible per the inclusion/exclusion criteria are allocated a subject number.

Visit 0 and visit 1 can be combined.

Test visits (V1, V2 and V3)

During test visit 1, the subject will be randomised to either treatment Arm A or Arm B and will be allocated a randomisation number. Hereafter the baseline questions will be completed by the Principal Investigator, or delegate. The subjects will be introduced to the clinical trial app and how to complete the questionnaires and take photos.

At test visit 1 and 2 investigational products (CE marked comparator products or non-CE marked Investigational Product) will be handed out according to the randomisation. The subject will only be informed about which product to wear in the upcoming period. At the visits the subjects will be trained according to the IFU, in preparation of the product (e.g. hole size), preparation of skin before application (e.g. cleaning and wiping), application of the product (e.g. correct position and applying pressure to the baseplate), removal of product and storage of the product.

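### The Safety population is defined by consent alone, so any percentage taken over it counts subjects who never used a study product

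*Combined protocol and SAP*

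**What the plan says.** Section 11.1 defines the set in one sentence: "The Safety population will constitute by subjects who have given informed consent". It sets no condition on randomisation or on use of a product. The same section then states that "adverse events and Device deficiencies will be assessed based on the safety population". By contrast, the ITT definition in that section requires both randomisation and exposure to a product.

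Section 6.4 fixes enrolment at consent: "A subject is considered enrolled in the investigation when the written informed consent is obtained". Section 6.3.1 describes two kinds of screening failure, and both have consented: "Screening failures are considered subjects that have signed the informed consent form and been included based on in- and exclusion criteria, but not yet randomised", and "Subjects that have signed the informed consent form but fails to comply with the in- and exclusion criteria are also considered screening failures". It adds that "Screening failures can be replaced by a new subject". Randomisation comes later, under section 7.1.1: "During test visit 1, the subject will be randomised to either treatment Arm A or Arm B". Products are first handed out at that same visit, which may be combined with the inclusion visit.

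On the safety analysis itself, section 11.1 says only that adverse events get a listing and, where relevant, a summary. Its general rules give N and percentage for discrete variables, over subjects or observations with non-missing data, and summaries by product where relevant. No denominator for a safety percentage by product is stated.

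**The concern.** A subject who consents and never uses a study product is not at risk of an event caused by one, yet the written rule puts that subject in the safety denominator. Screening failures are replaceable, so they come on top of the 96 to be randomised. Percentages of subjects with an adverse event or device deficiency would then be pulled downwards, which is the non-conservative direction. Safety of a product without CE marking is part of the stated aim (section 3), and adverse events and device deficiencies are the two safety endpoints (section 4.4.2).

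The cross-over adds a gap. Each subject uses one product per period, and someone who leaves in period 1 never uses the other. Section 4.1 also lets a subject who stops a period early go back to their own product until the next visit, so some time under observation is on neither study product. The plan does not say to which product an event belongs, or who counts as at risk for each product.

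**Working it through.** The plan states no adverse event rate, device deficiency rate or screening-failure count, so there is no figure of its own to reproduce. The check is first of membership, then of the size that different assumptions would give.

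**Membership.** Consent alone admits a subject to the Safety population (11.1). Both kinds of screening failure have consented (6.3.1). Randomisation and product hand-out follow consent (7.1.1). Unexposed subjects are therefore in the set whenever they exist. The non-missing-data rule does not clearly remove them, because safety is assessed at all visits and calls (7.1.4) and a consented subject can have a valid record of no event.

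**Overall dilution.** Let E be the number exposed to at least one product and S the number who consented but were never exposed. If the S subjects contribute no events:

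reported percentage = true percentage among the exposed × E/(E + S)

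E = 96 is the number to be randomised (4.1), taking all of them to use at least one product. S is assumed.

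| S (assumed) | E + S | Factor | A true 10% is reported as |
|---|---|---|---|
| 0 | 96 | 96/96 = 1.00 | 10.0% |
| 5 | 101 | 96/101 = 0.95 | 9.5% |
| 10 | 106 | 96/106 = 0.91 | 9.1% |
| 24 | 120 | 96/120 = 0.80 | 8.0% |

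S = 24 means that 24/120 = 20% of those consented are never exposed.

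For device deficiencies the assumption of no events among the unexposed is close to certain for screening failures, who have been handed no product. For adverse events, anything recorded between consent and first use would partly offset the dilution, but would then be counted without any exposure.

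**By product, if the whole set were used as each product's denominator.** The plan does not say that it would be. Section 11.2 allows for 20% drop-out. Assume that all of it falls before period 2 and is spread evenly over two arms of 48. Users of each product = 48 + 48 × 0.8 = 86.4. With S = 0 the factor is 86.4/96 = 0.90, so a true 10% is reported as 9.0%.

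As a bound on imbalance, put all the drop-out (0.2 × 96 = 19.2) in the comparator-first arm. The test product then has 96 − 19.2 = 76.8 users and the comparator 96. Equal true rates of 10% would read 7.68/96 = 8.0% and 9.6/96 = 10.0%.

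**The case against.** The plan promises no safety rate. It offers listings and, where relevant, summaries, with no incidence estimate and no between-product test of safety. Listings and counts are the same under either definition. Where tables are split by product, a never-randomised subject has no product and would naturally fall in neither column. A set defined by consent also has a proper use: enrolment starts at consent, and adverse events cover study procedures as well as the device (18.1), so collecting from consent loses nothing. The data review meeting before database lock classifies subjects into the populations. Finally, the pass/fail criterion rests on skin endpoints (11.4), and ongoing safety review works from individual events and lists (18.6.2.1 and 18.6.2.2).

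Most of this stands, and it limits the size and consequence of the problem. It does not repair the definition. The text sets a rule and assigns the safety endpoints to it. The meeting applies that rule, and rewriting it at that stage of an open-label trial would be post hoc.

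Two stronger readings are tempting. The first is that subjects who leave in period 1 do count in the second product's denominator. The plan is silent, so this is only a possibility. The second is that the understatement is large. Putting 120 consented subjects under each product together with the even drop-out above gives 86.4/120 = 0.72, or 7.2% for a true 10%. That figure stacks an assumed screening-failure share, drop-out entirely before period 2, and use of the whole set for each product. The documents make the first two less likely: eligibility is gone through by telephone before the consent visit (6.2), and a subject who cannot complete a period may move on to the next one instead of dropping out (4.1).

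**Conclusion.** The definition is wrong as a basis for percentages. It admits screening failures and other unexposed subjects, and nothing elsewhere in the plan adds an exposure condition. For any percentage of subjects with an event taken over the whole set, the direction is downward whenever unexposed subjects exist and contribute no events. For 96 exposed the factor runs from 1.00 (none unexposed) through 0.91 (10) to 0.80 (24). The counts are assumed, so the actual size is unknown and may be zero, for instance if nobody fails screening and every randomised subject uses a product.

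A reader might infer that the trial's safety rates will be materially understated, or that the comparison of products will be biased. The documents do not support either as a prediction, because they specify no such rates and give no unexposed count. For the cross-over, the finding is a missing by-product denominator and attribution rule that leaves room for the error. The point is worth correcting because safety is a stated aim and the correction is cheap, although no stated decision of the trial depends on these percentages.

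**What to change.** In section 11.1:

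- Define the Safety population, for summaries, as subjects who used at least one investigational product (test or comparator).
- Attribute each adverse event and device deficiency to the product in use at onset, and state how events that begin while a subject is on their own product are shown.
- For percentages by product, use as denominator the subjects who used that product.
- List separately the events and deficiencies recorded between consent and first use, so that none is lost.

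The accountability records in section 15 already call for subject identification and dates of use, so no new data are needed. The cost is a short change of text, slightly higher reported rates where unexposed subjects exist, and one extra listing.
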